#### Confidentiality Statement

Data and information contained in this document are considered to constitute trade secrets and confidential commercial information, and the legal protections provided to such trade secrets and confidential information are hereby claimed under the provisions of applicable law. No part of this document may be publicly disclosed without the written consent of Philip Morris Products S.A.

The Sponsor will provide training to the site staff prior to the study initiation related to the correct evaluation of this assessment. Subjects will also be trained on the correct evaluation of their puffing/inhalation behavior

#### 7.8.3 Weighing of P3P Products

At V2 and V6, P3P used for PK assessment should be weighed before product use and as early as possible (but within maximum 1 hour) after the end of product use. The balance precision needed for product weighing is at milligram (mg) level. The pre- and post- product use weight and time of weighing will be recorded in the CRF.

## 8 ADVERSE EVENTS

### 8.1 Definitions

#### 8.1.1 Adverse Events

An adverse event is defined as any health-related event which is adverse or unfavorable and which either starts after ICF signature or represents a worsening of a health-related condition that existed at the time of that signature. Careful medical judgment is required to establish whether a clinical finding (including an abnormal laboratory result) is a true AE or just a manifestation of a preexisting health-related condition. An AE may or may not have a causal relationship with the study procedures or with the use of investigational product.

#### 8.1.2 Serious Adverse Events

A serious adverse event (SAE) is defined as an AE that:

- results in death,
- is life-threatening,
- requires inpatient hospitalization or prolongation of existing hospitalization,
- results in persistent or significant disability/incapacity,
- is a congenital anomaly/birth defect, or
- is an important medical event

Important medical events that may not result in death, be life-threatening, or require hospitalization may be considered an SAE when, based on appropriate Investigator's medical judgment, they may jeopardize the subject or the subject may require medical or surgical intervention to prevent one of the outcomes listed in the above definitions.

"Life-threatening" means that the subject was at immediate risk of death from the event. It might have caused death if it had occurred in a more serious form.

#### 8.1.3 Conditions Existent Before the Start of the Period of Collection (ICF Signature)

Clinical conditions that existed before the start of the period of collection of AEs and still ongoing at V1 (concomitant disease), and whose severity or frequency remained unchanged after that point, should not be considered AEs and should not be captured as such. This includes medical therapies or surgical interventions that had been planned before the start of the period of collection regardless of involving admissions to hospital, if the medical condition to be addressed did not get worse after the start of the collection period. Otherwise, any medical condition that existed before the start of the period of collection and still ongoing at V1

---

#### Confidentiality Statement

Data and information contained in this document are considered to constitute trade secrets and confidential commercial information, and the legal protections provided to such trade secrets and confidential information are hereby claimed under the provisions of applicable law. No part of this document may be publicly disclosed without the written consent of Philip Morris Products S.A.

---

(concomitant disease) and whose severity or frequency increased after that point is to be captured as an AE or SAE, depending on the seriousness criteria met.

## 8.2 Collection and Reporting of Adverse Events

### 8.2.1 Collection of Information

Any non-serious AE occurrence during the study must be documented in the subject's medical records in accordance with the Investigator's normal clinical practice and on the AE page of the CRF. SAEs that occur during the study must be documented in the subject's medical record, on the AE CRF, and on the SAE form.

AEs should be collected mainly via face-to-face interview with the subject through spontaneous reporting or by the use of consistent, open, non-directive questions from the investigator(s) or designee(s) (e.g., "Have you had any health problems since you were last asked? or "How have you been feeling since you were last asked?").

Information recorded will include: verbatim description of the AE/SAE, start and stop dates, seriousness, severity (intensity), action taken (e.g., whether or not the AE/SAE led to the subject's discontinuation from the study), and outcome (e.g., resolved, stabilized).

Information to be recorded about an AE/SAE should include, whenever possible, onset and resolution dates and times, circumstances leading up to the event, clinical elements such as clinical course, specific vital signs and test results that may explain the pathophysiology of the event, as well as alternative explanations to its occurrence.

Whenever a medically meaningful diagnosis is available to comprise a set of reported signs and/or symptoms, it should be preferentially provided as the AE or SAE term, rather than the individual signs and/or symptoms. Otherwise, each one of those signs and/or symptoms should be reported separately as event terms.

### 8.2.2 Period of Collection

AEs (including SAEs) will be collected from the time of ICF signature until the EOS.

Any AEs which occur during the screening period will be captured by the study site staff and assessed by the Investigator or designee(s) in order to establish relationship to study procedures.

During a 14-day Safety Follow-Up Period new AEs/SAEs will be recorded and ongoing AEs/SAEs will be followed-up by the study site. In general, AEs will be followed-up until resolved, stabilized (i.e., no worsening of the event), or a plausible explanation for the event has been found and until the end of the study. At the end of the Safety Follow-Up all subjects will be contacted via phone in order to check the status of the ongoing AEs and also to collect any new AEs/SAEs experienced by the subjects. Subjects should be contacted 14-days after Day 30. In case they cannot be reached two additional attempts at the next 2 consecutive days will be made. If the subjects cannot be reached after the three attempts they will be declared

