## Definitions of Terms

End of Study	The end of the study (EOS) for a subject is defined as either the Discharge at Day 30, or the date of early termination of the subject, plus the Safety Follow-Up Period.  The end of the whole study corresponds to the individual EOS of the last subject.
Enrollment	On Admission Visit (Day -1) for eligible subjects after all applicable inclusion and exclusion criteria have been satisfactorily assessed and met.
Randomization	Allocation of the respective product, P3P-1mg or P3P-2mg, after product test on Day -1.
Screen failure	Subject who signs the ICF but is not enrolled at Admission.

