#### **Confidentiality Statement**

Data and information contained in this document are considered to constitute trade secrets and confidential commercial information, and the legal protections provided to such trade secrets and confidential information are hereby claimed under the provisions of applicable law. No part of this document may be publicly disclosed without the written consent of Philip Morris Products S.A.

stabilized (i.e., no worsening of the condition), or an acceptable explanation has been found (e.g., a chronic condition). The follow-up of the ongoing non-serious AEs will be done via a phone call performed at the end of the Safety Follow-Up Period.

At the end of the Safety Follow-Up Period, all ongoing non-serious AEs will be documented as “ongoing” and no further follow-up information will be sought on them by the Investigator. At that point, the Investigator will assess whether the subject should be referred to his/her General Practitioner to have their ongoing AEs addressed accordingly.

All SAE will be followed up by the Investigator or designee, despite their continuation after the end of the Safety Follow-Up Period, until their resolution, stabilization (i.e., no worsening of the condition), or an acceptable explanation has been found (e.g., a chronic condition).

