- q. At the end of Safety FU (end of V6 + 14 days) the site will call all subjects to collect new AEs/SAEs and to follow-up ongoing AEs/SAEs. If the subject is not responding at the initial call, 2 additional attempts on the next consecutive days will be made in order to reach the subject

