**Table 7: Categorical Variables Definitions Other Than Reported in eCRF**

Variable	Categories
Demographics	
BMI (kg/m ²)	Underweight: < 18.5 Normal range: ≥ 18.5 and < 25.0 Overweight: ≥ 25.0 and < 30.0 Obese: ≥ 30.0
Product Exposure Categories	≤ 5 P3P-1mg /Day $>5-10$ P3P-1mg /Day >10 P3P-1mg /Day ≤ 5 P3P-2mg /Day $>5-10$ P3P-2mg /Day >10 P3P-2mg /Day
Product Exposure Periods	
Detailed Product Exposure Periods	Product test Day 1 Day 2 Period 1 ([D3 –V3]) Period 2 ((V3-V4]) Period 3 ((V4-V5]) Period 4 ((V5-V6])
Overall exposure period	Day 1 to Day 29 inclusive

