12.5.9.1 Safety Reporting

An exposure emergent AE is defined as an AE that occurs after first product use or that is present prior to first product use and becomes more severe after first product use. All other AEs will not be summarized but provided in listings only.

Any AEs which occur after ICF signature will be captured by the site collaborators and assessed by the Investigator or designee in order to establish relationship or relatedness in respect to study procedures. The AE listings will include all AEs captured in the database at any time during the study (including those from subjects who were not in the safety population). All AEs occurring after the product test use will be included in the summary tables. During the screening period prior to the first product use, only study procedure related AEs will be listed.

AEs reported from enrolled subjects, but who did not start use on day 1 or later will be summarized in a separate listing: “Enrolled but not started randomized product use AEs”. Furthermore AEs reported after discharge on Day 30 are summarized in a separate listing ‘Safety follow-up AEs’.

If there are more than 10 AEs, the tables will also be split by product exposure period. The product exposure periods will be defined as below

Partial dates will not be imputed, but assumptions will be made as follows to assign to exposure-emergent or not:

Date information	Assign as
Partial date, e.g., --May2012, or ----2011. If month/year is the same as, or later than the month and/or year of first product use	Exposure-emergent
Partial date, e.g., --May2012, or ----2011. If month and/or year is earlier than the month and/or year of first product use	Not exposure-emergent

If exposure emergent adverse events cannot be attributed to P3P due to e.g. missing start time, the worst case principle will be applied : i.e. the event will be allocated to P3P use.

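### The follow-up call and the follow-up AE listing are dated from Day 30, while the follow-up period and end of study run from discharge or early termination

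*Protocol*

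**What the plan says.** **Follow-up period and AE window.** Protocol Definitions of Terms sets a subject's end of study (EOS) as "either the Discharge at Day 30, or the date of early termination of the subject, plus the Safety Follow-Up Period". Protocol 4.4 gives the same rule with 14 days, 4.1 (heading of the Safety Follow-Up paragraph) and 5.2 start the follow-up at discharge or early termination, and SAP section 4 defines Safety Follow-up in the same way. Protocol 8.2.2 closes AE collection at that point: "AEs (including SAEs) will be collected from the time of ICF signature until the EOS".

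**Date of the call.** Protocol 8.2.2 first says "At the end of the Safety Follow-Up all subjects will be contacted via phone" and then "Subjects should be contacted 14-days after Day 30". Protocol 4.1 and SAP 6.1 carry the same pair of sentences. Footnote q of Appendix A, in both documents, reads "At the end of Safety FU (end of V6 + 14 days) the site will call all subjects". Protocol 8.2.6 ties the call only to the end of follow-up: "The follow-up of the ongoing non-serious AEs will be done via a phone call performed at the end of the Safety Follow-Up Period".

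**SAP outputs.** SAP 12.5.9.1 defines listing 15.1.23.3 by "AEs reported after discharge on Day 30 are summarized in a separate listing" and does not mention early termination. It also splits AE tables by product exposure period when there are more than 10 AEs. It promises a definition of those periods, but what follows is a rule on partial dates. SAP Table 7 has exposure periods that end at V6, with an overall period of "Day 1 to Day 29 inclusive".

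**The concern.** An early terminator may have no Day 30 and no V6, yet every explicit date for the call uses one of these. A site that works from the dated sentence or the schedule footnote would call such a subject after the AE window has closed. That collides with two other rules. Protocol 8.2.6 has ongoing non-serious AEs recorded as ongoing at the end of follow-up, with nothing further sought, although this call is the check it specifies for them. After the window, 8.2.2 provides only for related SAEs that are reported spontaneously, so a non-serious event elicited by a late call, with onset after EOS, has no defined handling.

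Subjects discontinued because of an AE are on this path (Protocol 8.6), so what is at stake is tolerability data, a stated secondary objective. The SAP listing meant to show follow-up AEs uses the same Day 30 anchor.

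**Working it through.** **Stated figure.** The only stated figure that bears on these dates is the study duration per subject, 44 to 70 days (Protocol 4.4). It can be reproduced:

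- Minimum: 1 screening day + 1 admission day + 28 days (V6 two days early) + 14 = 44.
- Maximum: 21 + 1 + 32 (V6 two days late) + 14 + 2 further call days = 70.

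The components named in 4.4 alone give 21 + 1 + 30 + 14 = 66. Using the V6 window and the two extra call attempts to reach 70 is an assumption, as the documents do not show the build-up. The range describes completers and gives no date for early terminators.

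**Inputs for the gap.**

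- Call on the dated reading: 30 + 14 = Day 44 (Protocol 4.1, 8.2.2).
- AE window closes at EOS, 14 days after termination on Day D (Definitions of Terms, 4.4, 8.2.2).
- Earliest termination: Day −1, after the product test (Protocol 4.1).
- The schedule goes from Day −1 to Day 1 with no Day 0, so Day −1 plus 14 days is Day 14.

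**Formula.** For D ≥ 1, gap = 44 − (D + 14) = 30 − D. For Day −1, gap = 44 − 14 = 30.

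| Stops on | EOS | Gap, dated reading (days) | Gap, end-of-follow-up reading (days) |
|---|---|---|---|
| Day −1 (product test) | Day 14 | 30 | 0 |
| Day 1 | Day 15 | 29 | 0 |
| Day 7 | Day 21 | 23 | 0 |
| Day 15 | Day 29 | 15 | 0 |
| Day 22 | Day 36 | 8 | 0 |
| Day 29 | Day 43 | 1 | 0 |
| Day 30 (completer) | Day 44 | 0 | 0 |

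**Sensitivity.** Applying the ±2-day visit window to Day 30 makes the Day 1 gap 27 to 31 days and the Day −1 gap 28 to 32. Protocol 5.2 allows the early termination visit up to 7 days after discontinuation. If the 14 days start at that visit, the Day 1 gap falls to 29 − 7 = 22 days.

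**SAP listings, by group.**

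- Completers: AEs after the Day 30 discharge go to listing 15.1.23.3 as intended.
- Stopped before any use on Day 1 or later: SAP 12.5.9.1 gives them their own listing, 15.1.23.2.
- Randomized, used product, stopped early: no Day 30 discharge, so on the literal wording their follow-up AEs are not in 15.1.23.3. Events that are exposure-emergent are in listing 15.1.23.1 and in the summary tables.

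**AE tables by period.** If Table 7 supplies the missing definition, Period 4 ends at V6. A completer's follow-up, Days 31 to 44 (44 − 30 = 14 days), then belongs to no period. If Period 4 ends on Day 29, Day 30 has none either. Event counts by period would not sum to the overall count whenever an AE starts in those days.

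**The case against.** The strongest reply is that the late call is only one reading. The sentence just before the dated one puts the call at the end of the Safety Follow-Up, and the Synopsis and Protocol 8.2.6 do the same with no Day 30 date. For an early terminator that means termination plus 14 days, and the Day 30 sentence can be taken as the completer case. In 4.1 and 8.2.2 the reference to all subjects belongs to the end-of-follow-up sentence. Only footnote q joins it to V6, and that footnote also speaks of the end of follow-up. This stands: a reader might infer that early terminators will be called up to 30 days late, and the documents do not settle that. They leave two incompatible instructions, with the only explicit date on the completer side.

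A reader might also infer that early terminators' AEs vanish from the report. They do not. SAP 12.5.9.1 says that the AE listings cover every AE in the database, and SAP section 4 includes early termination in its definition of follow-up. On the dated reading, AEs from the call are reported after calendar Day 30, so their exclusion from 15.1.23.3 rests only on the subject having had no Day 30 discharge.

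The by-period problem depends on Table 7 being the intended definition and on more than 10 AEs occurring. It would be tempting to express the uncovered days as 14 of 44 (32%), but that is a share of calendar days and says nothing about the share of AEs.

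Finally, a reader might infer that an AE defined by a laboratory, spirometry or ECG result cannot be closed properly by telephone. That is a separate matter: 8.2.6 already has an unresolved non-serious AE recorded as ongoing, and nothing forces a resolved outcome.

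**Conclusion.** The point holds as an internal inconsistency. The follow-up period and EOS are anchored on discharge or early termination, while the explicit call date and the follow-up listing are anchored on Day 30 or V6. The size depends on which instruction the site follows: 0 days on one, 30 − D days on the other, with a maximum of 29 days for a randomized subject who used product. The 30-day case concerns only those who stop after the product test on Day −1, and their AEs have a listing of their own. These figures assume nominal visit days and a 14-day period that starts on the day of termination.

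In the SAP the consequence is misclassification in one listing and, if Table 7 is used, by-period event counts that need not add up. No AE that is reported is lost. On the dated reading, AEs of early terminators could be recalled late or missed. The documents give no expected number of early terminators, so how many subjects are affected cannot be estimated.

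**What to change.** - **Protocol 4.1, 8.2.2 and Appendix A footnote q; SAP 6.1 and Appendix A footnote q:** reconcile the call date to one anchor that matches the EOS definition, namely actual discharge or early termination plus 14 days. State whether early termination means the date of discontinuation or the date of the early termination visit, since Protocol 5.2 lets these differ by up to 7 days. Call and EOS then coincide for every subject.
- **SAP 12.5.9.1:** define listing 15.1.23.3 as AEs after discharge or early termination, in line with SAP section 4.
- **SAP 12.5.9.1 and Table 7:** supply the missing period definition for the AE tables, assign Day 30 explicitly, and add a post-exposure (Safety Follow-Up) period so that event counts by period sum to the overall count.

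The cost is wording in both documents and one more column in any AE table split by period. The number of calls and visits does not change.

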#### Confidentiality Statement

Data and information contained in this document are considered to constitute trade secrets and confidential commercial information, and the legal protections provided to such trade secrets and confidential information are hereby claimed under the provisions of applicable law. No part of this document may be publicly disclosed without the written consent of Philip Morris Products S.A.

lost to follow-up. Phone calls should be recorded in the source documents. Any AEs or SAEs that are ongoing at the end of the Safety Follow-Up Period will be managed as described in section 8.2.6.

SAEs spontaneously reported to the Investigator after the end of the Safety Follow-Up Period and considered related to the investigational product must also be reported to the sponsor.

### 8.2.3 Intensity of Adverse Event

The Investigator must assess the intensity of each reported AE according to the following grading scale:

**Table 3 Intensity of Adverse Events**

Mild:	Easily tolerated, not interfering with normal everyday activities
Moderate:	Interferes with normal everyday activities, but the subject is still able to function
Severe:	Incapacitating and requiring medical intervention

### 8.2.4 Relationship to Investigational Product and Relationship to Study Procedures

The Investigator must assess the causal relationship between the exposure to the IP and each of the reported AEs, using the classification system and the criteria described below. The same assessment must be made separately to assess the causal relationship between the study procedures and each of the reported AEs:

**Not related:** The temporal relationship of the adverse event to IP administration or study procedure(s) makes a causal relationship unlikely, or concomitant medication, therapeutic interventions, or underlying conditions provide a sufficient explanation for the observed event.

**Related:** The temporal relationship of the adverse event to IP or study procedure(s) makes a causal relationship possible, and concomitant medication, therapeutic interventions, or underlying conditions do not provide a sufficient explanation for the observed event.

### 8.2.5 Expectedness

Any AE assessed as related to the IP will be assessed for its expectedness. An AE will be regarded as “unexpected” if its nature or severity is not consistent with information already recorded about the IP P3P in section 6.5 of the current Investigator’s Brochure (22).

### 8.2.6 Follow-up of Non-serious and Serious Adverse Events

Any non-serious AE that is ongoing at the time of Discharge or early termination will be followed-up by the Investigator during the Safety Follow-Up Period until it has been resolved,

#### **Confidentiality Statement**

Data and information contained in this document are considered to constitute trade secrets and confidential commercial information, and the legal protections provided to such trade secrets and confidential information are hereby claimed under the provisions of applicable law. No part of this document may be publicly disclosed without the written consent of Philip Morris Products S.A.

stabilized (i.e., no worsening of the condition), or an acceptable explanation has been found (e.g., a chronic condition). The follow-up of the ongoing non-serious AEs will be done via a phone call performed at the end of the Safety Follow-Up Period.

At the end of the Safety Follow-Up Period, all ongoing non-serious AEs will be documented as “ongoing” and no further follow-up information will be sought on them by the Investigator. At that point, the Investigator will assess whether the subject should be referred to his/her General Practitioner to have their ongoing AEs addressed accordingly.

All SAE will be followed up by the Investigator or designee, despite their continuation after the end of the Safety Follow-Up Period, until their resolution, stabilization (i.e., no worsening of the condition), or an acceptable explanation has been found (e.g., a chronic condition).

